3.2 Secondary Objectives

The secondary objectives of the study are to determine whether genicular artery embolization is effective in improving

1. Knee pain using an electronic VAS at 1-, 3-, and 12-months (and final 18-48 months visit) post intervention
2. Knee pain using WOMAN pain score at 1- and 12-months (and final 18-48 months visit) post intervention
3. Knee stiffness using the WOMAC knee stiffness score at 1-, 3-, and 12- months (and final 18-48 months visit) post intervention
4. Physical function using the WOMAC function score at 1-, 3-, and 12- months (and final 18-48 months visit) post intervention
5. Self-reported quality of life using EQ-5D-5L scale at 1-, 3-, and 12- months (and final 18-48 months visit) post intervention [28]
6. Synovitis on MRI at 3 months post intervention

Other secondary objectives are to assess

1. Feasibility / technical success defined as successful selective catheterization of target vessel(s) and embolization from at least one feeding artery of the knee joint (with the embolization endpoint defined as suppression or reduction in the filling of (and therefore blood flow in) abnormal vessels visible on angiography).
2. Reduction in frequency of pain medication usage over 30-day period assessed at baseline and at 1, 3, and 12 months follow-up visits post intervention (acetaminophen, over the counter NSAIDs, prescription NSAIDs, opioids)
3. Reduction in frequency of knee injection therapy over 12-month period (assessed at baseline and at 12-month follow-up visit post intervention)
4. Reduction in frequency of need for physical therapy over 12-month period (assessed at baseline and at 12-month follow-up visit post intervention)
5. Safety evaluated by cumulative rates of adverse events (AE), as well as type and severity of each adverse event.

4 Study Design and Endpoints

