
1- If not previously available (i.e., recent knee MRI within 3 months of screening); if MRI cannot be obtained on the same day due to subject preference and/or MRI scheduling related reasons, MRI can be performed anytime between the baseline visit and intervention visit
 
2- If not previously available (i.e., recent knee radiograph within 6 months of screening). Can be performed on a separate day based on appointment availability or subject's preference.
 
3- Post-procedural MRI can be done on a separate day of visit 6 based on appointment availability and subject's preference as long as it's performed within the timeframe of 3month +/- 10 days.
 
* Visit 1 and 2 can be combined based on subject preference. In that case, procedures listed in visit 2 will be performed after signing informed consent on the same day.
 
** Visit 4 (1-day follow-up) dates range can be +3 days (phone call, telemedicine, or in-person IR clinic visit determined by subject's preference and need for physical examination)
 
*** Visit 8. Optional visit for participants who completed 12 month follow up by August 31, 2024 (by invitation, voluntary, and after obtaining informed consent for this visit). This visit can be performed at any time interval within 18 months – 48 months
								

CONFIDENTIAL

post procedure. This visit can be performed by sending the questionnaire by a safe email and participants can email it back to research coordinator or PI OR by a phone call performed by research coordinator,
	
# 1, 3, 12-month follow-up dates range can be +/- 10 days
	
## The pre-procedural blood work can be done on the day of the procedure prior to performing the procedure based on subject's preference.
	
--	--	--	--

1 Key Roles

- **Principal Investigator (PI):** Will be one of two interventional radiologists performing the procedure. Will be responsible for study integrity, data monitoring, data collection, statistical analysis, and manuscript writing.

[name]

Clinical Assistant Professor of Radiology
Director, Vascular and Interventional Radiology Research Program
Department of Radiology, NYU Langone Health
[name]
[contact]
Email: [contact]

- **Co-PI:** Co-investigator involved in recruiting patients and conducting the clinical assessment for knee osteoarthritis

[name]

Associate Professor
Department of Internal Medicine, NYU Langone Orthopedic Center
[name]

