2.4 Potential Risks & Benefits

2.4.1 Known Potential Risks

Potential adverse events related to the use of the device from the device from the device insert of directions for use (DFU) [attachment 1] and recent literature [6, 23]:

- Possible adverse events:
 - Incomplete occlusion of vascular beds or territories may give rise to the possibility of post-procedural development of alternative vascular pathways, recanalization, or recurrence of symptoms
 - Post-embolization syndrome including fever, malaise, headache, and myalgia (body aches)
 - Transient, self-resolving cutaneous purpura / skin color change
 - Transient plantar or peripheral sensory paresthesia
 - Synovitis related symptoms including pain, stiffness or limited joint mobility
- Rare adverse events:
 - Allergic reaction and foreign body reactions (e.g., pain, rash, fever, inflammation)
 - Capillary bed saturation and tissue damage
 - Infection
 - Neurological deficits
 - Pulmonary embolization
 - Thrombosis
 - Undesirable reflux, passage/migration or placement of Embozene™ Microspheres, resulting in non-target embolization, ischemia, and / or ischemic infarction.
 - Non-target embolization to lower extremity vasculature resulting in vascular thrombosis and limb threatening ischemia
 - Vessel or lesion rupture
 - Tissue necrosis
 - Dermal ulcer
 - Tendon or ligament rupture
 - Osteonecrosis (rare- not reported in prior studies)
 - Joint infection (rare- not reported in prior studies)

- Very rare adverse events:
 - Cerebrovascular accident (CVA)
 - Death
- Potential adverse events associated with angiography and catheterization of vessels include:
- Nausea, vomiting, and/or allergic reaction anaphylaxis due to iodinated contrast used during embolization procedure (less possible)
 - Contrast-induced renal dysfunction (less possible)
 - Access site-related adverse events: bleeding, infection, hematoma formation, arteriovenous fistula, pseudoaneurysm (rare)

CONFIDENTIAL

- Vessels catheterization associated adverse events: injury to catheterized vessels including vessel perforation, dissection, vasospasm, or thrombosis (rare)
- Infection (rare)

Potential adverse events associated with radiation exposure due to use of knee radiograph and fluoroscopy

- Deterministic radiation risks: Radiation-induced injuries to the skin and underlying tissues, which occur shortly after the exposure (rare)
- Stochastic radiation risks: Radiation-induced malignancy which may occur later in life (rare)

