4.2.2 Secondary Study Endpoints Analysis

Secondary efficacy endpoints are:

- 1- WOMAC pain score at 1- and 12- months (and final 18-48 months visit) post intervention
- 2- Pain electronic VAS at 1-, 3-, and 12- months (and final 18-48 months visit) post intervention
- 3- Knee stiffness WOMAC score at 1-,3-, and 12- months (and final 18-48 months visit) post intervention
- 4- Physical function WOMAC score at 1-, 3-, and 12- months (and final 18-48 months visit) post intervention
- 5- Total WOMAC score at 1-,3-, and 12- months post intervention
- 6- Self-reported quality of life using EQ-5D-5L scale at 1-, 3-, and 12- months (and final 18-48 months visit) post intervention.
- 7- MRI findings at 3- months post intervention
- 8- Pain medication usage at 1-, 3-, and 12- months (and final 18-48 months visit) post intervention
- 9- Injection therapy requirements (hyaluronic acid or steroid) at 12- months (and final 18-48 months visit) post intervention
- 10- Physical therapy requirements at 12- months (and final 18-48 months visit) post intervention
- 11- Feasibility / technical success
- 12- Laboratory findings at 1-, 3-, and 6- months (and final 18-48 months visit) post intervention

Secondary safety endpoints are:

- 13- Number/rate, severity, and description of complications, adverse events, or poor outcomes that are secondary to the procedure, which will be summarized using counts and simple statistics (i.e., mean number of patients with complications.)

CONFIDENTIAL

5 Study Enrollment and Withdrawal

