7.1 Study Procedures/Evaluations

7.1.1 Study Specific Procedures

- Medical history
 - Complete medical history will be obtained from medical records if available and/or by interview during clinic visits.
- History of previous and concomitant treatment
 - Knee injections and frequency over the 12 months
 - Medication history over the last month will be obtained during pre and post intervention study visits. Medication history will focus on medications currently taken for the treatment of knee OA; including prescription and over-the-counter medications for pain.
 - Physical therapy and frequency over the 12 months
 - Weight loss / gain
- Focused physical examination:
 - Vital signs (temperature, blood pressure, heart rate, oxygen saturation, height, weight, BMI)
 - Focused knee examination.
 - Lower extremity pulses
- Imaging assessment with knee MRI
 - Baseline and follow-up (at 3 months) knee MRI will be performed.
 - Knee MRI protocol will include: Axial t2 FS, Sagittal PD, Sagittal T2 FS, Coronal PD FS, Coronal PD FS, non-contrast axial and sagittal T1 FS.
 - Imaging variables collected for this study is found in the attached eCRFs
- A discussion of the results of any study specific procedures (e.g., radiographic or other imaging or laboratory evaluations) will be provided to participant after the completion of the study unless these information represent a significant health-related issue.
- Laboratory tests:
 - Baseline and follow-up (at 1-, 3-, and 12-, 18-48 months) laboratory tests will be obtained
- Administration of questionnaires or other instruments for patient-reported outcomes:
 - Electronic VAS
 - KOOS questionnaire
 - Self-reported quality of life EQ-5D-5L questionnaire

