7.3.2 Enrollment/Baseline (Visit 2, Day -29 to -1)- In interventional radiology clinic

- Verify informed consent of potential participant (study consent)
- Verify subject's eligibility
- Targeted physical exam
- Administration of study questionnaires
- Previous / concomitant treatments
- Baseline MRI (if one is not available within the last 3 months)
- Baseline knee radiograph (if one is not available within the last 6 months)
- Peripheral venous blood draws and urine sample (baseline laboratory tests)
- Note: Subjects will be required to withhold pain medications 24 hours prior to screening and each visit for the evaluation of pain

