7.3.3 Interventional visit (visit 3, Day 0)

- Within 30 days of visit 1
- Verify informed consent of participant verified by signature on written informed consent
- Geniculate artery embolization
- Record any immediate complications / adverse events detected during the procedure or observation period (if applicable)
- Subjects will be given a phone number to reach a physician 24 hours a day to report any adverse symptoms and receive medical advice

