7.3.4.2 Follow up visit at 1-month (Visit 5, Day 30 +/- 10)

- Obtain medical history
- Record adverse events as reported by participant or observed by investigator (if applicable)
- Targeted physical exam
- Administration of study questionnaires
- Previous / concomitant treatments, including medical history
- Peripheral venous blood draw and urine sample to perform follow-up laboratory tests

CONFIDENTIAL

- Note: Subjects will be required to withhold pain medications 24 hours prior to screening and each visit for the evaluation of pain

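### A 1-month visit held before Day 30 counts days before the procedure as post-treatment pain-medication use

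*Combined protocol and SAP*

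**What the plan says.** Section 3.2 sets the look-back for analgesic use: "Reduction in frequency of pain medication usage over 30-day period assessed at baseline and at 1, 3, and 12 months follow-up visits post intervention". Section 4.2.2 lists the matching endpoint: "Pain medication usage at 1-, 3-, and 12- months (and final 18-48 months visit) post intervention". Section 7.1.1 says how it is collected: "Medication history over the last month will be obtained during pre and post intervention study visits".

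The timing comes from section 7.3. The procedure is at "Interventional visit (visit 3, Day 0", the baseline visit at "Enrollment/Baseline (Visit 2, Day -29 to -1", and the first outcome visit at "Follow up visit at 1-month (Visit 5, Day 30 +/- 10" days. A footnote to the Schedule of Activities repeats the tolerance: "1, 3, 12-month follow-up dates range can be +/- 10 days".

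Section 10.4.3 promises an estimate and 95% confidence interval for each secondary outcome at each visit and for its change from baseline. Measures other than the WOMAC and VAS scores are to be handled as yes/no outcomes with a McNemar test, and daily analgesic use is given as an example. Section 10.1 says that no formal SAP will be written.

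**The concern.** The look-back and the nominal visit day are both 30 days long, so the period fits only if the visit is on Day 30 or later. The permitted window opens on Day 20. For an earlier visit, part of what is labelled post-treatment use took place before the patient was treated. That part cannot respond to the procedure and carries the patient's value back toward baseline. The amount depends on the appointment date, which has nothing to do with benefit.

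At stake is the 1-month change in analgesic use, which section 10.4.3 commits the study to report. With no SAP planned, no later document is due to correct the definition.

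**Working it through.** **Inputs.** Look-back L = 30 days (sections 3.2 and 7.1.1, reading a month as 30 days). Visit 5 on day v, from 30 - 10 = 20 to 30 + 10 = 40 (section 7.3.4.2). Procedure on Day 0 (section 7.3.3). Baseline visit on day b, from -29 to -1 (section 7.3.2). The plan states no figure for this endpoint, so there is nothing to reproduce first.

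**Step 1: untreated days in the 1-month look-back.** The look-back covers Days v - 30 to v - 1. Days before the procedure = max(0, 30 - v).

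| Visit 5 on | Look-back | Days before procedure | Share of 30 |
|---|---|---|---|
| Day 20 | -10 to 19 | 10 | 33% |
| Day 25 | -5 to 24 | 5 | 17% |
| Day 29 | -1 to 28 | 1 | 3% |
| Day 30 | 0 to 29 | 0 | 0% |
| Day 40 | 10 to 39 | 0 | 0% |

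**Step 2: how often.** The documents do not give the spread of visit days. If it were uniform over the 21 permitted days (assumption), 10/21 = 48% of visits would include untreated time, and the mean would be (10 + 9 + ... + 1)/21 = 55/21 = 2.6 days.

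**Step 3: double counting.** The baseline look-back covers Days b - 30 to b - 1. Its overlap with the visit 5 look-back is max(0, b + 30 - v). With b = -1 and v = 20 it is 9 days (Days -10 to -2). With b = -10 or earlier it is 0, even for a Day 20 visit.

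**Step 4: effect on a rate.** Suppose a patient uses analgesics on a fraction p0 of days before the procedure and p1 after it, each constant (assumption). For v below 30 the measured rate is [(30 - v)p0 + v p1]/30, so the measured change is (v/30)(p1 - p0). At Day 20 that is 20/30, or two thirds of the true change. The documents give neither p0 nor p1, so the absolute size is unknown.

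**Step 5: effect on the yes/no outcome.** This depends on a definition that section 10.4.3 does not supply. Under an any-use rule, a patient who used analgesics until the procedure and then stopped counts as a user at any visit whose look-back reaches back to a day of use, and as a non-user from Day 30 on. Under a strict every-day rule the same patient counts as improved on every visit day; such a rule could instead hide someone who becomes a daily user only after the procedure.

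**Step 6: later visits.** The earliest 3-month look-back starts on Day 80 - 30 = 50 and the earliest 12-month one on Day 350 - 30 = 320. Neither reaches the procedure.

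**The case against.** The best answer is that little depends on this. It concerns one time point of one secondary objective in a single-arm pilot. The average contamination may be only 2.6 of 30 days. On a days-of-use scale the pull is toward no effect, so it does not manufacture a benefit. Section 7.4 also records concomitant pain medication on eCRFs, which might separate use before and after the procedure, and the collection forms are not among the documents and may define the period differently. All of this limits the consequence. None of it removes the mismatch: section 7.4 does not say that dates of use are recorded, and the protocol text contains no rule that stops the look-back at Day 0.

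A reader might infer more than the documents support:

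- **That the days just after embolization must also be excluded.** Section 2.4.1 lists "Post-embolization syndrome including fever, malaise, headache, and myalgia (body aches" and synovitis-related symptoms as possible adverse events. But those days are genuine post-treatment time, and section 7.1.1 focuses the history on medicines taken for knee OA. Counting them is a defensible choice. A shorter window at month 1 alone, such as 14 days, would weaken comparison with months 3 and 12.
- **That one clinical course scores very differently by visit date.** A patient using analgesics daily through Day 6 and never again would score 17/30 at Day 20, 7/30 at Day 30 and 0/30 at Day 40, that is, reductions of 43%, 77% and 100%. This rests on an assumed seven days of peri-procedural use and on a count of days. Under the planned yes/no analysis the patient could count as improved on all three dates.
- **That benefit will falsely appear to grow from month 1 to month 3.** This is speculation. In the 72-patient cohort cited in section 2.2.2, mean WOMAC pain fell from 6.2 at 1 month to 4.4 at 4 months, so a growing benefit could be real.

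**Conclusion.** The point holds in a limited form. With a 30-day look-back and a visit permitted from Day 20, every 1-month visit on Days 20 to 29 counts between 1 and 10 untreated days as follow-up. Up to 9 of them can also sit in the baseline period when baseline falls just before the procedure. This follows from the stated dates, provided that the recall period is a literal 30 days and the unseen forms do not override it.

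For those visits the measured change is pulled toward none. The one-third attenuation at Day 20 applies only to a days-of-use rate with constant use before and after the procedure. The bias in the reported 1-month result cannot be computed: use rates, actual visit days and the definition of daily use are all missing. The 3- and 12-month results are sound on this point, and so is the medication condition in the primary responder rule, which is assessed at 3 months.

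**What to change.** In sections 3.2 and 10.4.3, state that the visit 5 look-back starts no earlier than Day 0. Express use as days of use divided by post-procedure days observed, with denominator min(v, 30): 20 days at a Day 20 visit, and 30 from Day 30 on. Compare it with days of use divided by 30 at baseline. If the McNemar analysis is kept, derive its yes/no category from the same rate. The 30-day period stays as it is at 3 and 12 months, and no exclusion of the early post-procedure days is required.

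Section 7.3.5 shows that the study is well advanced, so many 1-month histories may already have been taken. Where use was not dated, report the actual day of visit 5 and add a sensitivity analysis limited to visits on or after Day 30.

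The cost is a sentence in each of the two sections. The earliest visits rest on 20 observed days instead of 30, and the sensitivity analysis loses patients. If visit days were uniform (assumption), 11 of the 21 permitted days qualify, or about 40 x 11/21 = 21 of the planned 40 patients.

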4.1 Description of Study Design

This study is a single-center, single arm, no sham or placebo, open label, prospective pilot study designed to evaluate the safety and feasibility of geniculate artery embolization for the treatment of knee OA. Enrolled patients will receive angiography and embolization of the one or more geniculate arteries in the affected knee using 250 µm Embosphere microspheres. If both knees are affected, the knee with the higher pain score on electronic VAS will be targeted.

The primary objective is to evaluate the effectiveness of geniculate artery embolization in reducing knee pain at 3 months. The primary objective will be evaluated by the clinical success rate. Clinical success is defined as at least 50% reduction in WOMAC pain score at 3-month follow up visit. 40 patients will be required for this study. The study would accrue 50 patients to account for an attrition rate of 20%.

Change in WOMAC pain score and pain VAS will be used as a measure of efficacy (i.e., pain reduction).

WOMAC questionnaire is a widely used, disease-specific measure for knee OA. It includes 24 questions on daily activities. WOMAC pain score includes five questions regarding pain (pain during walking, stair climbing, nocturnal, rest, weight bearing); each question will be scored using the

CONFIDENTIAL

following points: 0 for no pain, 1 for mild, 2 for moderate, 3 for severe, and 4 for extreme pain. possible score ranges for pain are 0–20. For this purpose, WOMAC Score will be calculated from the Knee injury and Osteoarthritis Outcome Score (KOOS) score which was developed as an extension of the WOMAC score with the purpose of evaluating short-term and long-term symptoms and function in subjects with knee injury and osteoarthritis. This means that the KOOS questionnaires will be administered to patients during visits and the WOMAC score will be calculated from the KOOS scores later at the time of data analysis.

The electronic VAS is a horizontal line with no markings on the scale except “No pain” on the left (score: 0 mm) and “worst possible pain” on the right end of the scale (score: 100 mm). Subjects mark the VAS to indicate their current pain level, with 0 mm representing “No pain” and 100 mm representing “worst possible pain”. In our study, subjects will be asked to mark their pain level on a paper VAS on study questionnaire form and will give a score between 0 to 100, which will be documented on the appropriate eCRF.

All study variables will be collected on paper form [forms # 1-7 attached to this protocol] and study questionnaire forms (source documents) at the time of each clinic visit and transferred to eCRFs (TrialMaster; on NYU Langone secure servers) by the study coordinator or an investigator. The source documents (paper forms) will be placed in secure locked folders with study documents (such as signed consent forms). The data dictionary of TrialMaster will be similar to the attached forms , [attachment 5].

4.2 Study Endpoints

4.2.1 Primary Study Endpoints

The primary endpoint is WOMAC pain score at 3 months post intervention.

4.2.2 Secondary Study Endpoints Analysis

Secondary efficacy endpoints are:

- 1- WOMAC pain score at 1- and 12- months (and final 18-48 months visit) post intervention
- 2- Pain electronic VAS at 1-, 3-, and 12- months (and final 18-48 months visit) post intervention
- 3- Knee stiffness WOMAC score at 1-,3-, and 12- months (and final 18-48 months visit) post intervention
- 4- Physical function WOMAC score at 1-, 3-, and 12- months (and final 18-48 months visit) post intervention
- 5- Total WOMAC score at 1-,3-, and 12- months post intervention
- 6- Self-reported quality of life using EQ-5D-5L scale at 1-, 3-, and 12- months (and final 18-48 months visit) post intervention.
- 7- MRI findings at 3- months post intervention
- 8- Pain medication usage at 1-, 3-, and 12- months (and final 18-48 months visit) post intervention
- 9- Injection therapy requirements (hyaluronic acid or steroid) at 12- months (and final 18-48 months visit) post intervention
- 10- Physical therapy requirements at 12- months (and final 18-48 months visit) post intervention
- 11- Feasibility / technical success
- 12- Laboratory findings at 1-, 3-, and 6- months (and final 18-48 months visit) post intervention

Secondary safety endpoints are:

- 13- Number/rate, severity, and description of complications, adverse events, or poor outcomes that are secondary to the procedure, which will be summarized using counts and simple statistics (i.e., mean number of patients with complications.)

CONFIDENTIAL

5 Study Enrollment and Withdrawal

